**Protocol #: 16-1932**

**Project Title: Helping moms to be healthy after baby**

**Principal Investigator: [name] [name]**

**Version Date: 09/08/2017**

**Hypotheses and Specific Aims:**

This protocol outlines details for both a main study and a Substudy.

Main study hypotheses:

1. The multicomponent novel weight loss intervention delivered in WIC will be feasible and acceptable.
2. This intervention will be associated with a greater weight change over 12 weeks compared to control.

Main study aims:

**Aim 1:** To evaluate the feasibility and acceptability of a multi-component novel weight loss intervention delivered in a WIC setting to a population of low-income, predominantly racial/ethnic minority, obese, postpartum women.

**Aim 2:** To evaluate differences in weight change between intervention and control participants to determine preliminary intervention efficacy over a 12-week period.

SUBstudy hypotheses:

1. The multicomponent novel weight loss intervention delivered in WIC will be acceptable.
2. This intervention will be associated with differences in diet, physical activity, and self-efficacy compared to control

SUBstudy aims:

**Aim 1:** To evaluate the acceptability of a multi-component novel weight loss intervention delivered in a WIC setting to a population of low-income, predominantly racial/ethnic minority, obese, postpartum women.

**Aim 2:** To evaluate differences in diet, physical activity, and self-efficacy, between intervention and control participants to determine preliminary intervention efficacy over a 12-week period.

## **II. Background and Significance:**

Low-income and minority women are at increased risk for postpartum weight retention (i.e. retaining weight after pregnancy) and consequent persistent obesity. Women who have had children, especially racial/ethnic minority women who have had children, have 3 times the risk of obesity compared to women who have not had any children. Pre-pregnancy obesity is an important contributor to postpartum weight retention. Women who are obese pre-pregnancy are 3-5 times more likely to gain weight, rather than lose weight, in the postpartum period than non-obese women. Addressing maternal weight during this time is critical given that obesity places women at increased risk for poor health outcomes (e.g. cardiovascular disease) and their offspring at increased risk for obesity. Addressing maternal weight in the first year postpartum is essential given evidence that weight retained beyond this period is usually retained long-term and is an independent risk factor for obesity.

Effective interventions addressing postpartum weight retention in low-income and racial/ethnic minority women are urgently needed. Translation of evidence on weight loss to the postpartum period in a community setting is lacking, yet holds great potential. WIC is an ideal location to translate such evidence given that WIC, staffed by educators and registered dietitians (RDs), interacts regularly with women in the postpartum period, offering nutrition education and supplemental foods.

Obesity science supports that weight loss interventions should be multi-component with regular points of contact. Building upon this, we have designed a multi-component intervention that considers the demands on women in the postpartum period and utilizes technology for both provider decision support and for virtual contact with participants. The intervention will address diet, physical activity, and social support through the use of in-person meetings with WIC staff, text messaging, phone coaching, and Facebook. In-person meetings with WIC staff will occur monthly in addition to the typical quarterly appointments, and will focus on the mother vs. the more common emphasis primarily on the infant. HeartSmartMoms, an electronic provider decision support tool, which our team previously piloted in a WIC-based intervention (Puma et al, under review), will assist providers in using motivational interviewing (MI). MI has been shown to enhance weight loss. Text messaging has also been used to enhance weight loss through the use of motivational messages as well as the encouragement of self-monitoring. In-between monthly WIC visits, women will receive daily texts. Phone coaching will also be available. Finally, women will join a private WIC Facebook group where they can receive information from WIC educators and connect with other intervention participants for social support. Text messages, phone coaching, and Facebook were endorsed by WIC clients and will offer flexibility throughout the day as to when participants engage with intervention components.

## **III. Preliminary Studies/Progress Report:**

We conducted 4 focus groups with WIC clients (2 English and 2 Spanish). There was overwhelming support for the desire to have additional support for postpartum weight loss in the WIC setting. Women liked HeartSmartMoms and thought it could be helpful. Most women were open to having WIC visits focused more heavily on maternal lifestyle habits. Women were open to getting information via texts, some women wanted phone coaching, and women who used Facebook, liked the idea of connecting online with other mothers of young infants enrolled in WIC.

Co-investigators have experience in weight loss both clinically and in research studies. [name] has been involved in multiple studies focused on post-partum weight loss including protocols using lifestyle coaching.

## **IV. Research Methods**

### **A. Outcome Measure(s):**

#### **Main study:**

##### **Primary:** Feasibility and acceptability:

- We will assess the ease of recruiting women for the study (number enrolled/number approached) and attrition from the study.
- We will also collect data on intervention adherence, including number of women who received the entire intervention, number of women who came to visits, use of HeartSmartMoms (HSM), participation in self-monitoring, use of phone coaching, and use of the Facebook group page.

##### **Secondary:**

- Change in weight over 12 week period

#### **Substudy:**

##### **Primary:** Feasibility and acceptability:

- We will conduct semi-structured interviews with intervention participants at the 12 week time point to understand their experience in the intervention and to obtain feedback on each component.

##### **Secondary:**

- Dietary saturated fat, trans fat, total sugars, "added sugars", fruit and fruit juice, vegetable intake, glycemic load and glycemic index
- Physical activity
- Self-efficacy related to diet and exercise
- Readiness to change
- Eating stimulus index

### **B. Description of Population to be Enrolled:**

#### **Main study:**

We will be working with low-income, English or Spanish-speaking postpartum mothers enrolled in the Aurora WIC clinic. The Aurora WIC clinic serves predominantly minority women; nearly 70% of women are racial/ethnic minorities. To be eligible for WIC, women must be low-income or  $\leq 185\%$  of the poverty level.

This population was chosen because they are at high risk for obesity in the postpartum period and weight retention and prolonged obesity.

Inclusion criteria:

- Adult woman ( $\geq 18$  and  $< 50$  years old)
- Enrolled in WIC or with an infant enrolled in WIC;
- 3-12 months postpartum
- A pre-pregnancy BMI of 25 - 40 kg/m^2 (based on self-reported height and weight prior to pregnancy)
- Postpartum body mass index between 25 and 50 kg/m^2
- English- and/or Spanish-speaking
- Owns a mobile phone with texting functionality
  - In order to receive texts during the trial

Exclusion criteria:

- Health conditions impacting weight or ability to participate in a weight loss trial
  - Pregnancy or planned pregnancy in next 5 months
  - Any health problems or undergoing any treatments that might interfere with what participant eats or her ability to exercise
  - Medical provider recommendation to avoid exercise
- Plans to be in a different geographic area within the next 5 months
- Plans to stop coming to Aurora WIC in the next 5 months.
- Unable to give informed consent;
- Not able to read and understand English or Spanish at an 8th grade level.
- Not willing to create a Facebook account if they do not already have one.
- Asked to follow-up in  $< 3$  months at most recent WIC visit

Substudy:

The substudy will have 2 parts – Part A and B. Part A applies to the lifestyle group from the main study and will have 2 phases (1 and 2). This is split into 2 phases so that Phase 2 opportunity and the associated financial remuneration of Phase 2, is not known until the 12 week visit. We want a true assessment of the participation in the lifestyle intervention as it would be run in WIC, and thus do not want participants to stay in the intervention solely for the remuneration in the substudy. Part B applies to the observation group in the main study.

Part A Phase 1

Inclusion criteria:

- Participant in the lifestyle group in the Main study presenting for baseline visit

Exclusion criteria:

- None

Part A Phase 2

Inclusion criteria:

- Participant in the lifestyle group in the Main study presenting for 12 week visit
- Participated in Part A Phase 1

Exclusion criteria:

- None

## Part B

### Inclusion criteria:

- Participant in the observation group of the main study presenting for baseline visit

### Exclusion criteria:

[figure not shown]
- None

## C. Study Design and Research Methods

Main study: We propose a pilot randomized controlled trial. We will pilot a multicomponent intervention delivered in a WIC setting. In order to attempt to model the intervention as it would be run in WIC, there will be no remuneration for participating other than the small gift (\$5) at the beginning of the study.

Substudy: Women in the main study will be eligible for this substudy. The substudy is broken into 2 Parts (A-Lifestyle group from Main study , B- observation Group from Main study). We will ask participants to complete a survey and for some a semi-structured interview.

Here is an overview of our study process

**Setting:** The study (main and substudy) recruitment/enrollment, intervention delivery and data collection will occur at the Aurora WIC clinic. Over a year ago we partnered with WIC and over the last year developed this study protocol together, with input from WIC clients. All study activities will occur at this site except for data management, some phone/text contact with interested individuals/participants, and data analysis.

### **Participant Recruitment, Screening, and Enrollment:**

#### Main study:

We will enroll up to 80 women, with a goal of 40 to complete the substudy Part A phase 2 or Part B. We will post flyers in the WIC office regarding the study opportunity and WIC staff will wear tags about the study (optional for WIC staff to wear)— see Appendix Q and R.

The UCD PRA will review the WIC records for upcoming appointments for each day and pre-identify those women who are 3-12 months postpartum. She will share the list of those with appointments meeting this criteria with the WIC staff, reminding them to introduce the study opportunity to the person at the end of the appointment.

WIC staff will introduce the study to postpartum women at the end of a visit to WIC. Before introducing the study to a person, the WIC staff person will screen for 3 eligibility criteria using data available to her. 1) Person is 3-12 months postpartum, 2) WIC is not recommending to come back to WIC prior to 3 months, and 3) if data is available, person meets current BMI eligibility. If the person meets these criteria, the WIC staff member will introduce the study to the person. They will also give them the flyer (Appendix C) with more information about the study and the screening questions for the person to review (Appendix A.2 page 1 only). This screening done by the WIC staff member ensures that the study is not offered to women who are not eligible based on data already available at WIC.

We will recognize WIC staff efforts to present the study to WIC clients meeting the above criteria by giving \$5 gift cards. These gift cards will be given on about a weekly basis to WIC staff demonstrating active engagement in supporting the study. This includes, but is not limited to those presenting the study the most frequently to WIC clients, having a positive attitude about the study, or encouraging other WIC staff to help recruit for the study.

Women interested in learning more will then immediately meet with the PRA. If they cannot meet with the PRA, they will be offered times to return to meet with the PRA. An appointment will be set to meet with the PRA. If the WIC staff person making this appointment to meet with the PRA is not on the study protocol, then a text reminder will be sent to the interested person the day before their visit with the PRA. The text will be sent through the automated text reminder system used by WIC. No identifying information will be shared with the study team. If the person assisting the person in making an appointment with the PRA is on the study protocol, then they will offer a phone or text reminder to the participant from the study team, asking permission to share their name and phone number with the study team. If the person agrees to this, a text reminder (or phone call if preferred) will be sent to the person the day prior to their appointment to remind them about their appointment. This will be sent from the study team texting platform. No identifying information will be included in the text. If the person does not show up to their scheduled appointment, the study team will send a follow-up text asking if the person would like to reschedule the appointment.

During the meeting, the PRA will read the prescreening consent (Appendix A.1) and then assess eligibility using a series of questions and calculating the BMI after measuring the person's weight and height. (Appendix A.2) The questions address specific inclusion/exclusion criteria for the main study to assess eligibility and suitability for study participation. To ensure confidentiality, we will not record any identifiers on the screening questionnaire (Appendix A.2). We will retain the screening questionnaires as detailed in the screening consent language (Appendix A.1). The data on these sheets will help us to understand why people were not eligible. No identifying information will be written on the screening questionnaire

If the person is eligible, the RA will educate the person on the study procedures. To help with comprehension, the RA will give the participant a page with more in-depth study information, and a consent form (Appendix N and E).

The bilingual (English/Spanish) RA will describe the study in-depth and answer all questions. This will occur 1 on 1 or with multiple interested individuals at the same time. After answering all questions,

the RA will meet 1 on 1 to address any further questions the person may have about the study. The RA will then read the consent form to the person, who will have their own copy to read along. The consent contains information about the study procedures and risks. It also recommends that participants should check with their medical provider before starting to exercise. We will NOT require individuals to bring in a note from their medical provider. The RA will answer any questions as needed. For those ready, the RA will complete the informed consent process and enroll the person in the study. As part of the consent process, participants will be offered to take additional time if needed to decide. If they need additional time, they will be asked to call the RA if they decide they are interested in participating. If this happens, they will be asked to come meet in person with the RA at the WIC office to complete the informed consent process and enroll in the study. We will stress during this informed consent process that participation in our research study is voluntary, that subjects may withdraw from the study at any time, and that the investigators reserve the right to discontinue the research protocol at any time. A copy of the signed informed consent form will be given to each subject. Appendix E is the main study consent form.

The Aurora WIC sees over 700 women monthly. Over 50% of these women report being overweight or obese pre-pregnancy. Given these high numbers and the importance of this topic to women in WIC (as described by WIC clients during prior stakeholder meetings), we expect to complete enrollment within a 2-4 month time period.

Treatment assignment: Following informed consent, women will be randomly assigned to the lifestyle group (intervention) or observation group (control). We will use a computer program to randomize subjects using block randomization, to ensure equal numbers of intervention and control participants, given the small sample size. We will randomize in blocks of 10 using a random number generator where 1= intervention (Lifestyle group) and 2= control (Observation group). The RA will have sealed envelopes labeled and ordered from 1 up. The RA will open the next envelope in order of consenting to assign the participant to the intervention or control arm.

### Substudy:

The substudy will be broken into 2 parts: Part A for Lifestyle group participants and Part B for the Observation group participants. Data collection varies slightly between these 2 groups as outlined in the study procedures. Only persons participating in the Main study are recruited to be in the Substudy. Screening for eligibility will be done by the PRA based on assigned group in the Main study. Enrollment will occur as follows:

Part A for lifestyle group involves completing 2 phases.

Part A: Phase 1 (labeled Part A.1) involves survey data collection around the time of the Main study's Baseline visit. This will occur either at the visit when the person is consented into the main study or at the baseline visit. After the person is consented into the main study and randomized to the lifestyle group, they can then complete data collection for the main study. Once this is done, they will then be offered the opportunity to participate in this substudy. If they are interested, the RA will conduct informed consent using the information sheet Appendix F.A.1.

Part A: Phase 2 (labeled Part A.2) involves survey and interview data collection at the Main study's 12 week visit. After completing data collection for the Main study at the 12 week visit, the PRA will introduce this study opportunity. If the person is interested, the RA will then complete informed consent, using the information sheet Appendix F.A.1., and enroll the person into the study.

These 2 phases will be presented to participants at these different time points in order to ensure that the substudy opportunity is not an incentive to participate in the main study.

Part B for the observation group involves survey data collection at both the baseline and 12 week visit. This substudy opportunity for data collection at 2 time points will be offered to participants at the baseline visit. If the person is interested, the RA will then complete informed consent, using the information sheet Appendix F-B, and enroll the person into the study.

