## Study procedures:

### Main study:

In this randomized controlled study participants will be randomly assigned to either an observation group (control) or a Lifestyle group (intervention). Both groups will receive the following:

1. Two visits to the WIC office for data collection as described below (Baseline and at 12 weeks).
2. Study visit reminder calls and/or texts either or both ~1 week and ~1-3 days before baseline and the 12 week study visit.
3. A small gift (less than \$5 in value) at the baseline visit.

For each subject, the time from enrollment to study completion will be approximately 12-20 weeks, depending on timing of scheduling of the visits.

Baseline and 12 week study visits and parameters to be measured on all participants:

At the baseline study visit, we expect data collection to take < 30 minutes. We will collect data using a survey and anthropometric measurements.

- **Survey:** We will orally administer the survey (Appendix B) to participants to avoid literacy issues that are common in low-income populations. Survey questions will include the following:
  - a. Demographics: Maternal age, education level, race, ethnicity, marital status, employment status, number of children, age of youngest child (months), ages of children at home, and acculturation level. To measure acculturation, we will use an adapted version of the Spanish and English language-use subscales of the Bidimensional Acculturation Scale for Latinos. Each subscale contains 5 items about language use, with responses ranging from never (1) to always (5).
  - b. We will also ask about smoking, formula and breastfeeding, and whether the mother has been or is diabetic or prediabetic, mother's weight before her recent pregnancy, and whether she is currently participating in any weight loss programs or is pregnant.

- c. Contact information: We will ask for her name, address, phone numbers, email address, and contact information for someone we can call if we cannot reach the participant. We will ask her to identify the number she wants to receive texts and the email address where we send the Facebook invite, if she is in the Lifestyle group.
- **Anthropometrics:** Weight and height measured twice using WIC scales and stadiometer.

At the 12 week study visit, we expect data collection to take about 20 minutes, collecting anthropometric measurements and some survey data.

**Anthropometrics:** Weight and height measured twice using WIC scales and stadiometer.

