All participants													
Data collection – in-clinic	X												X
Lifestyle Group participants only													
In-clinic intervention visits using HeartSmartMoms and lifestyle coaching using motivational interviewing	X				X				X				
Outgoing texts 2-7/week		X	X	X	X	X	X	X	X	X	X	X	
Facebook group participation		X	X	X	X	X	X	X	X	X	X	X	
Pedometer use	X	X	X	X	X	X	X	X	X	X	X	X	
Weekly send in weight and step count		X	X	X	X	X	X	X	X	X	X	X	
Weekly phone coaching		X	X	X	X	X	X	X	X	X	X	X	

Please note: We will do our best to schedule visits 4 , 8 and 12 weeks after the baseline visit. However, given possible scheduling conflicts, we will allow a 2 week window around each of the visits.

Contacting participants for their study visits:

We will contact participants to schedule future study visits (baseline, 4, 8 and 12 weeks for lifestyle group participants and baseline and 12 weeks for observation group participants) by phone/text in order to schedule these visits. If we are unable to reach them by phone/text, we will use email and mail. Additionally, during the consent process, we will get permission from subjects to contact a family member or friend if we are having trouble getting in touch with the subject at any point in the study. We will use these methods if phone, text, mail, email do not work. Participants will also get text reminders about upcoming visits. If participants fail to show up for an appointment, we will contact them to reschedule.

WIC benefits: WIC administration of benefits to participants in this study will be as follows.

Observation Group: No changes for the Observation group participants.

Lifestyle Group: Standard practice at WIC is to administer benefits to WIC clients for the time period between visits. In other words, if a WIC client is scheduled to be seen in 3 months, then she would receive 3 months of benefits. If she is asked to be seen in 1 month, she will receive one month of benefits. We plan to mirror this in the Lifestyle group. Participants in the lifestyle group

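### The substudy baseline survey may be taken at the consent visit in the lifestyle arm but only at the baseline visit in the observation arm, so survey change scores can cover different lengths of time

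*Combined protocol and SAP*

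**What the plan says.** Section IV.C, Participant Recruitment, Screening, and Enrollment, Substudy, sets the timing of the baseline survey separately for each arm.

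- **Lifestyle arm (Part A Phase 1):** "This will occur either at the visit when the person is consented into the main study or at the baseline visit". The preceding sentence places this survey at roughly the time of the main study's baseline visit, with no limit in days or weeks. On the order of events it says: "After the person is consented into the main study and randomized to the lifestyle group, they can then complete data collection for the main study". The substudy is offered after that.
- **Observation arm (Part B):** "Part B for the observation group involves survey data collection at both the baseline and 12 week visit", and "This substudy opportunity for data collection at 2 time points will be offered to participants at the baseline visit". No consent-visit option is given.

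The entry criteria in Section IV.B use the baseline visit in both arms. Part A Phase 1 admits a "Participant in the lifestyle group in the Main study presenting for baseline visit", and Part B admits a "Participant in the observation group of the main study presenting for baseline visit".

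Three other places bear on timing. Section IV.C, Study procedures, Main study, states that "the time from enrollment to study completion will be approximately 12-20 weeks, depending on timing of scheduling of the visits". It also lists reminders before the baseline visit, so baseline can be a separately scheduled appointment. The note under the table of study activities says: "We will do our best to schedule visits 4 , 8 and 12 weeks after the baseline visit", with a 2-week window. The Data Analysis Plan (Section IV.F) compares the arms by Student t-test and mentions no adjustment for elapsed time.

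**The concern.** Aim 2 of the substudy compares the arms on diet, physical activity and self-efficacy over 12 weeks. Eating stimulus and readiness to change are measured at the same two visits. A change score is comparable between arms only if the first measurement is taken at the same point relative to the last. Here the assigned arm determines which visits may supply the first measurement. Randomization does not remove such a difference, because it arises after assignment, and truthful answers do not remove it either.

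Women enter at 3 to 12 months postpartum, when eating, activity and infant feeding may change without any intervention. A lifestyle woman surveyed some weeks before baseline contributes those untreated weeks to her change score. An observation woman does not. Some ordinary change over time could then appear as a difference between arms.

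**Working it through.** **Step 1. The rules by arm.**

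| Item | Lifestyle | Observation |
|---|---|---|
| Survey timing, enrollment text (IV.C) | consent visit or baseline visit | baseline visit |
| Entry criterion (IV.B) | presenting for baseline visit | presenting for baseline visit |
| Data collection table (IV.C) | one baseline column | same column |
| 12-week visit counted from | baseline visit | baseline visit |

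The arms differ only in the first row. There the lifestyle rule also conflicts with the lifestyle entry criterion, which would not yet admit a woman at the consent visit unless that visit is also her baseline visit.

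**Step 2. How far consent can precede baseline.** The plan states no consent-to-baseline interval, so its range of about 12-20 weeks cannot be rebuilt from components. It can be used to bound the gap:

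gap = (enrollment to completion) - (baseline to 12-week visit)

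Reading the window as plus or minus 2 weeks, baseline to the final visit is 12 - 2 = 10 to 12 + 2 = 14 weeks.

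- Total 20, final visit at week 14: 20 - 14 = 6 weeks.
- Total 20, final visit at week 12: 20 - 12 = 8 weeks.
- Total 12, final visit at week 12: 12 - 12 = 0 weeks, which is consent and baseline on the same day.

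If the window means plus or minus 1 week, the late-visit case is 20 - 13 = 7 weeks. An early final visit at week 10 would leave 20 - 10 = 10 weeks, but that pairs the longest total with the earliest final visit and I do not rely on it.

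**Step 3. Span of the survey change score.**

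- Observation: 10 to 14 weeks.
- Lifestyle, surveyed at baseline: 10 to 14 weeks.
- Lifestyle, surveyed at consent: the same interval plus the gap, up to about 20 weeks in total.

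**Step 4. Average effect on the lifestyle arm's span.** Mean extra span = share surveyed at consent x gap. The plan gives neither quantity, so these values are assumptions chosen to show the range.

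| Share | Gap (weeks) | Mean extra span (weeks) | Relative to 12 weeks |
|---|---|---|---|
| 25% | 2 | 0.25 x 2 = 0.5 | 0.5 / 12 = 4% |
| 50% | 4 | 0.50 x 4 = 2 | 2 / 12 = 17% |
| 100% | 8 | 1.00 x 8 = 8 | 8 / 12 = 67% |

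The last row is the extreme case. With same-day visits every entry is zero. These are weeks of follow-up, not units of outcome. The documents give no rate of untreated change for any survey measure, so the calculation stops here.

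**Step 5. Whether the analysis absorbs the difference.** The t-test described in Section IV.F has no term for elapsed time. I read its comparison of lifestyle habits as a comparison of change from baseline, as it is stated for weight. If 12-week levels were compared instead, baseline timing would not enter.

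**The case against.** The strongest reply is that the enrollment text already keeps Phase 1 near the baseline visit, so a survey taken six or more weeks earlier would not fit its intent. That has force, and it makes the longest gaps less plausible. But the phrase sets no limit, and the sentence that follows it allows the consent visit without requiring that baseline be close.

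Efficacy is also a secondary, preliminary aim, and the sample size was set for the feasibility aim. That stands, and it keeps the point minor.

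A reader might infer three stronger points that the documents do not support.

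- **Baseline weight is brought forward in the lifestyle arm only.** The enrollment text gives an order (main-study data, then the substudy offer), which could suggest this. But Study procedures, Main study, places weight at the baseline visit for all participants, and nothing sets a different rule for observation women. The wording on weight is ambiguous and does not establish a difference between arms.
- **The bias can be put in kilograms.** That needs a weekly drift in weight, a gap and a share of women affected, none of which the plan gives. It would also quantify weight, where the difference in timing is not established. Even the direction is open: the Background notes that women who were obese before pregnancy are more likely than others to gain weight postpartum.
- **A lifestyle woman surveyed at consent who never returns distorts the Aim 2 comparison.** She has no 12-week value and so no change score. She affects only the count of substudy entrants.

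**Conclusion.** The point holds for the substudy survey outcomes: diet, physical activity, self-efficacy, eating stimulus and readiness to change. Read literally, the enrollment text permits a longer change period in the lifestyle arm than in the observation arm, and it conflicts with the plan's own entry criterion. The extra time for an affected woman runs from zero to about 6 to 8 weeks. This rests on the upper end of an approximate range, a final visit at week 14 or 12, and a plus or minus 2-week window. How many women would be affected is not stated, and the size and direction of any resulting bias are unknown. For weight, the text needs only to be brought into line with Study procedures. Severity is minor, and no sample-size figure changes.

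**What to change.** In the Part A Phase 1 paragraph of the enrollment section (IV.C), delete the consent-visit alternative so that the sentence names only the baseline visit. Both arms then give the baseline survey and baseline weight at that visit, as Section IV.B and Study procedures already indicate. The planned span becomes 12 weeks in each arm, or 10 to 14 with the window. If the sponsor wants to keep a consent-visit option, allow it in both arms and only when the baseline visit is held the same day.

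In either case, record the dates of the survey and the weight measurement for every participant, so that the actual interval can be checked and reported by arm.

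The cost is one wording amendment and two date fields. The downside is small: lifestyle women lose the chance to complete the 30-45 minute survey at an earlier visit.
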